2.4 STUDY AIMS/HYPOTHESES

NULL HYPOTHESIS. 10Hz tACS does not decrease immune response compared to active sham.

ALTERNATIVE HYPOTHESIS. 10Hz tACS decreases immune response compared to active sham.

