5.2 STIMULATION SESSIONS

Participants will undergo two sessions with the same procedure; the only change will be the stimulation condition.

5.4.1 SESSION 1

In the initial session, participants will be explained the procedure and reminded of their expectations and rights (informed consent). After obtaining consent, a urine drug test and pregnancy screening will be administered. Once they are both determined to be negative, the stimulation, EEG, and heart rate electrodes will be applied. Participants will then undergo a ten-minute resting state block to record EEG activity. Participants then provide a baseline saliva sample and receive 40 minutes of either 10Hz tACS or sham stimulation (depending on the randomized condition) while watching the 'Reefscape' video. After the stimulation, the participant will complete the stimulation adverse effects questionnaire, and will then provide a final saliva sample. The study coordinator will remove all equipment, and the participant will fill out the final two questionnaires and receive \$20 in compensation.

5.4.2 SESSION 2

The procedure for the second session will follow the same timeline as the first, with the exclusion of informed consent, urine drug test, and pregnancy screening processes. Participants will receive \$40 in compensation at the end of this session.

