6 STUDY PROCEDURES/EVALUATIONS

6.1 SELF-REPORT MEASURES

During the telephone screening, researchers will collect demographics, which include medical history and medication history. In addition, several other self-report measures will be used throughout this study. These measures are listed below and can be found in the attached documents.

- A. THE PERCEIVED STRESS SCALE (PSS) is a 10-item self-report assessment using a 5-level Likert scale to assess the degree to which an individual perceives life events as stressful in the past month. This scale is the most commonly used measure of self-reported stress, and produces results that are valid for 4-8 weeks after administration (Cohen & Williamson, 1988).
- B. THE STATE-TRAIT ANXIETY INVENTORY (STAI) is a 20-item self-report assessment that assesses either temporary or chronic anxiety. For the purposes of this study, the state version will be used to measure anxiety as a result of the stress condition. The STAI is commonly used to assess both types of anxiety, and has applications in both clinical and research settings (Spielberger et al, 1983).
- C. THE BEHAVIORAL INHIBITION AND BEHAVIORAL APPROACH SYSTEM SCALES (BIS/BAS) are a set of 24 questions used to assess an individual's sensitivity to approach vs. inhibition in motivating behavior. This scale is commonly used to measure behavior and has been demonstrated to be reliable (Carver & White, 1994).
- D. THE CONNOR-DAVIDSON RESILIENCE SCALE (CD-RISC) is a 25-item self-report assessment using a 5-level Likert scale to assess the degree of resilience an individual displays to stressful events. This scale has been shown to be a reliable measure of resilience, correlating with improvement during treatments designed to improve anxiety disorders (Connor & Davidson, 2003).
- E. THE POSITIVE AND NEGATIVE AFFECT SCHEDULE (PANAS) is a 20-item self-report assessment using a 5-level Likert scale to assess the positive and negative affect of an individual over the past week. This scale has been shown to be a reliable measure of both positive and negative affect with little subjectivity to demographic variables (Watson et al, 1988).

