6.4.2 SALIVA SAMPLES

We will be collecting a saliva sample at the first session. This sample will be used to test for a single nucleotide polymorphism in the BDNF gene whose presence may have an influence on effectiveness of brain stimulation. Within the central nervous system, BDNF regulates survival, proliferation, and synaptic growth as well as directly influences synaptic plasticity in the adult human brain (Antal et al., 2010). Egan et al. (2003) demonstrated that Val66Met, a single nucleotide in the BDNF gene, has function consequences in healthy humans, including decreased episodic memory and hippocampal inducing a reduction in recall capacity. This polymorphism is common in over one third of the Caucasian population (65% Val66Val to 35% Val66MET) (Pezawas et al, 2004; Hariri and Weinberger, 2003). Kleim et al. (2006) found that individuals with the Val/Val polymorphism respond to tDCS and transcranial magnetic stimulation (TMS) treatments with expected change, whereas, individuals expressing Val/MET allele do not. These authors indicate the difference to be caused by the impairment in synaptic plasticity caused by the Val/MET allele. These findings suggest that individual efficacy of treatments using brain stimulation may be partially genetically predetermined and should be taken into account when performing such procedures. Accordingly, we will conduct genotyping of all participants in this study in order to assess BDNF status. We will perform exploratory analyses in which we group participants by BDNF status.

We will also be collecting two saliva samples at each session to test for a cytokine panel, salivary alpha-amylase, and cortisol as measures of immunity and stress.

INSTRUCTIONS FOR SPECIMEN PREPARATION, HANDLING, AND STORAGE. The saliva samples for BDNF testing will be collected using 2mL DNA collection kit from DNA Genotek. Before sample collection, it is imperative that the participant does not eat, drink, smoke or chew gum for at least 30 minutes before providing a sample. Once the participant provides the 2mL sample, the collection tube is closed and a liquid from the lid will be released into the tube. The original lid will be removed and replaced with a small cap and the tube will be agitated for 5 seconds. The sample is then returned to the plastic packaging and labeled with the date of collection, the study name, and the participant ID. These samples are kept in a secure location until the completion of data collection.

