8.2 POTENTIAL RISKS

8.2.1 PSYCHOLOGICAL

Emotional Distress: As part of data collection, participants will undergo a timed mental arithmetic task designed to induce psychological stress. This task is meant to induce a short-term stress response via enhanced secretion of catecholamines. Such a response occurs naturally in the body and has not shown any long-term negative side effects. In order to protect the integrity of results, participants will not be made aware of the purpose of the task until after completion of the final session.

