11.1 STATISTICAL ANALYSIS STRATEGIES

11.1.1 MEASURES OF INTEREST

The primary outcomes of this study will be the quantified changes in cytokine, alpha-amylase, and cortisol activity.

EEG changes will be quantified and analyzed as secondary outcomes.

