11.1.2 ANALYSIS

Statistical analyses will be performed to test the null hypothesis indicated in section 2.4 *Study Aims/Hypothesis*. Data from the saliva samples will be compared within and between the two treatment sessions for each participant. Within sessions, the post-treatment sample will be compared to both the post-stress and the baseline, to determine the changes in biomarker levels as a result of the stimulation. Then, these two differences will be compared to the same differences from the corresponding treatment session for the participant, in order to determine if the tACS treatment had a significant effect on NK cell count. Biomarkers will also be correlated with each other to confirm the previously established relationship between sympathetic activation and immune response.

A significant difference (p -value less than or equal to 0.05) between the treatment conditions in within-session activity of any of the biomarkers will constitute a rejection of the null hypothesis. Any outcome with a p value > 0.05 will be regarded as inconclusive. Confidence intervals of 95% will be reported for all statistical estimates. Additionally, interpretation of outcomes will focus on estimated changes in levels of biomarkers, rather than just significance. Data will be represented in a mixed linear model to account for correlated data and unequal variances. In the event that the primary outcomes do not produce significant results, exploratory analyses will be conducted on the existing data to determine new hypotheses.

Any incomplete or missing data will be excluded from analysis; if time permits, further data collection will be conducted to account for the loss.

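### One directional null is rejected if any of at least three primary biomarkers differs at an unadjusted p ≤ 0.05, so the false-rejection rate is uncontrolled: about two to three times that of a single test of the same form

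*Combined protocol and SAP*

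**What the plan says.** Section 2.4 sets out one null: "NULL HYPOTHESIS. 10Hz tACS does not decrease immune response compared to active sham". Its alternative is a decrease.

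Section 11.1.1 names several primary outcomes and ranks none of them: "The primary outcomes of this study will be the quantified changes in cytokine, alpha-amylase, and cortisol activity". Section 6.4.2 says that the saliva collected at each session is used to "test for a cytokine panel, salivary alpha-amylase, and cortisol as measures of immunity and stress". It does not say how many cytokines the panel holds, or which assays stand for immunity and which for stress.

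Section 11.1.2 (Analysis) undertakes to test the section 2.4 null and gives the rule: a significant difference at p ≤ 0.05 "between the treatment conditions in within-session activity of any of the biomarkers will constitute a rejection of the null hypothesis". It states no sidedness, and no multiplicity adjustment appears in the protocol. The same section promises 95% confidence intervals for all estimates and puts the emphasis of interpretation on the size of the changes.

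The number of contrasts per marker is not settled. Section 11.1.2 says that within a session "the post-treatment sample will be compared to both the post-stress and the baseline". Section 8.2.1 says that "participants will undergo a timed mental arithmetic task designed to induce psychological stress", and section 6.1 says of the anxiety inventory that "the state version will be used to measure anxiety as a result of the stress condition". The session description in section 5.2 contains no stressor: "Participants then provide a baseline saliva sample and receive 40 minutes of either 10Hz tACS or sham stimulation", followed by one final sample. Section 6.4.2 and Appendix A likewise provide two biomarker samples per session.

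**The concern.** The rule makes one claim and gives it several chances to succeed. Any one of three or more markers is enough, and each is tested at the full 0.05. The chance of rejecting when stimulation does nothing is therefore higher than for one test, by an amount that the plan neither limits nor states.

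Two further gaps come from the same sentence. First, the null concerns a decrease while the rule asks only for a difference, so read literally an increase would reject a null of no decrease. Second, the null concerns immune response while the rule accepts any biomarker, so a change in cortisol or alpha-amylase with no cytokine change would also reject.

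At stake is what a reported rejection would mean. Section 11.1.2 (Aims) says that the outcomes will inform whether a larger trial is run, and a rejection by this rule would be weaker evidence than its p-value suggests.

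**Working it through.** The documents give no familywise error rate, power or sample size calculation, so there is no figure of the plan's own to reproduce.

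**Inputs from the documents.** Threshold 0.05 per test, unadjusted (section 11.1.2 Analysis). At least m = 3 primary markers (section 11.1.1), counting the cytokine panel as one test. A crossover in 20 participants (sections 3 and 4).

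**Assumptions.** Correlations of 0, 0.5 and 0.8 between markers, because none is given. Normal, equally correlated paired differences and complete pairs. A one-sample t-test on the 20 paired differences (19 degrees of freedom) stands in for the mixed model.

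**Step 1: independent tests.** P(at least one rejection) = 1 − 0.95^m = 1 − 0.95³ = 1 − 0.857 = 0.143.

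**Step 2: correlated tests, by simulation.** Three tests, one contrast, no effect on any marker:

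| Reading of the rule | One test | Corr. 0 | 0.5 | 0.8 |
|---|---|---|---|---|
| Two-sided, either direction rejects (literal) | 5% | 14% | 13% | 10% |
| One-sided at 0.05 for a decrease | 5% | 14% | 12% | 9% |
| Two-sided p, only decreases count | 2.5% | 7% | 6.5% | 5% |

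The ratio to a single test of the same form runs from about 3 at correlation 0 (14/5; 7.4/2.5) to about 2 at 0.8 (10/5; 5/2.5).

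**Step 3: what the literal reading lets in.** Of the 14.3% at correlation 0, 6.9 points are rejections on increases only, and 9.3 points are rejections without the cytokine. At correlation 0.8, of 9.9%, these are 5.0 and 4.9 points. The two groups overlap.

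**Step 4: more tests, conditional only.** If both contrasts in section 11.1.2 were tested on three markers, with an assumed correlation of 0.5 between contrasts, the two-sided rate would be about 25% / 22% / 18%. With assumed panels of 4 or 10 cytokines and one contrast, it would be 26% / 21% / 14% (6 tests) or 46% / 33% / 19% (12 tests).

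**Step 5: effect of Holm over three tests.** The chance of any rejection under no effect becomes 5.0% / 4.5% / 3.6% if two-sided and either direction counts. If only decreases count, it is about 2.5% / 2.3% / 1.8%.

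**Step 6: power.** With noncentral t and n = 20, the standardised paired difference (dz) detectable with 80% power is 0.66 at two-sided 0.05 and 0.78 at 0.05/3, the first Holm step. The one-sided values are 0.58 and 0.71. If all three markers truly fall by dz 0.5, one two-sided test has 56% power. The any-marker rule then rejects with probability 1 − (1 − 0.564)³ = 0.917, about 92%, at correlation 0, and 81% and 72% at 0.5 and 0.8. With Holm these become about 75% / 63% / 53%.

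**The case against.** The best case for leaving the text alone is that this is a 20-person pilot with no sample size calculation. It claims no overall 5% rate, reports confidence intervals and emphasises estimated changes. The rule says openly that any biomarker will do, so a careful reader is not misled, and for a screening study a missed signal may cost more than a false one. The Aims tie the larger-trial decision to the outcomes in general and not to this rule. All of that stands, and it limits the consequence. It does not remove the rule: the emphasis on estimates is added alongside the rejection sentence and does not replace it.

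Because the analysis is said to test the directional null of section 2.4, one can also fairly read it as an ordinary two-sided p-value with only decreases counting. The three-test rate is then 7% down to 5%. A reader might take 10% to 14% as the full range, and the documents do not support that. Even so, the rate remains two to three times the 2.5% of a single such test.

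A reader might also infer that the plan fails to say which markers count. It does say: any of them. What is unsettled is whether cortisol and alpha-amylase belong under immune response. Treating them as stress markers only is an inference, since section 6.4.2 describes the assays jointly.

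**Conclusion.** The point holds, with modest consequence. The rule gives one null at least three unadjusted chances of rejection and carries over neither the direction of section 2.4 nor its restriction to immune response. With three tests, the false-rejection rate lies between about 5% and 14%, depending on sidedness and on an assumed correlation of 0 to 0.8. If one-sided tests for a decrease were intended, the direction gap closes but the inflation remains.

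Two stronger readings are not supported. The plan does not misstate its error rate, because it states none; the rate is uncontrolled, not misreported. Nor can the rates of 14% to 46% in step 4 be attributed to the plan. The panel size is not given, and the post-stress sample that the second contrast needs is not scheduled. Those rates show only that three tests is the lowest count.

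**What to change.** First reconcile sections 5.2, 6.4.2 and Appendix A (two biomarker samples per session, no stressor) with sections 6.1, 8.2.1 and 11.1.2 (a stress condition, a stress task, a post-stress sample). The number of contrasts follows from that. Then replace the rejection sentence in section 11.1.2.

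- **Preferred for this pilot:** drop the rejection rule. Report each biomarker's within-session change under 10 Hz tACS minus the same change under sham, with a 95% confidence interval, labelled exploratory. The cost is the formal test.
- **If a formal test is kept:** list the primary markers, including the panel members, and the contrasts, and apply Holm across all of them. State sidedness: either one-sided tests for a decrease at a familywise 0.05, or two-sided at 0.05 with only decreases counting, accepting a true rate of about 2.5% or less. Either limit rejection to cytokines or reword section 2.4 to include stress markers. For three two-sided tests the cost is a rise in detectable dz from 0.66 to 0.78. If all three markers fall by dz 0.5, the chance of at least one rejection drops from about 92% / 81% / 72% to 75% / 63% / 53%.
- **A single primary marker** needs no adjustment, but in the same scenario gives about 56%. That is well below the any-marker rule and, at correlation 0.8, slightly above Holm. It also requires choosing the marker in advance, so it is a trade-off for the sponsor.

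Each option is a few sentences of text and needs no new data. If a post-stress sample proves to be intended, scheduling it is a cost of resolving the contradiction and not of this change.

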11.2 SAMPLE SIZE DETERMINATION

This clinical trial represents a pilot study. A pilot study is a clinical trial that is conducted to decide whether a new treatment should be tested in a large controlled trial; therefore, we do not calculate sample size. This study can be

considered a pilot study, as it is the first time this specific treatment will be performed on this clinical population. The results from this study will be used to determine sample sizes for future, large-scale clinical trials.

In addition, we have to restrict the number of included participants to a small sample size due to limited funding resources.

12 DATA HANDLING AND RECORD KEEPING

The study coordinator and research assistants are responsible for the accuracy, completeness, legibility, and timeliness of the data reported.

12.1 PHI AND HIPAA

Information about study participants will be kept confidential and managed according to the requirements of the Health Insurance Portability and Accountability Act of 1996 (HIPAA). Those regulations require a signed subject authorization informing the subject of the following:

- What protected health information (PHI) will be collected from the participants in this study
- Who will have access to that information and why
- Who will use or disclose that information
- The rights of a research subject to revoke their authorization for use of their PHI.

In the event that a participant revokes authorization to collect or use PHI, the investigator, by regulation, retains the ability to use all information collected prior to the revocation of participant authorization. For participants that have revoked authorization to collect or use PHI, attempts should be made to obtain permission to collect at least vital status (i.e., that the subject is alive) at the end of their scheduled study period.

12.2 CONFIDENTIALITY

Data will be stored in a password-protected cloud-based data system that does not contain any patient information. Individual records are referred to by dummy identifiers that cannot be traced back to the study participants except with the master code list that is stored separately in a secured location. Source documents (i.e. paper forms) will be kept in a locked file cabinet in a locked office. The key linking dummy identifiers with participant information will be securely located separate from all other data collected, and will never appear in an electronic format.

12.2.1 ACCESS TO SOURCE DOCUMENTS

The research coordinator, research assistants, and PI will have access to all of the source documents collected over the course of the study.

Data will stay on a password-protected computer. Subsequently, a copy will be processed on a separate, password-protected desktop computer in the [name] Lab ([name]).

12.2.2 SENSITIVE INFORMATION

Sensitive information may be collected during the screening process in order to determine eligibility (medical history, recreational drug use, etc.). Such information will be de-identified and stored in a secure, locked file cabinet, and will not be used in any further proceedings in the study.

12.2.3 OTHER

Please note that there is no significant risk of deductive disclosure in this study. In addition, none of the groupings or subgroupings used in analysis will be small enough to allow individuals to be identified.

12.3 SOURCE DOCUMENTS

Source data is all information, original records of clinical findings, observations, or other activities in a clinical trial necessary for the reconstruction and evaluation of the trial. Source data are contained in source documents.

Source data include:

PARTNERS HUMAN RESEARCH COMMITTEE (IRB).

- All IRB correspondences are documented
- The study staff is IRB approved prior to performing any study procedures
- Adverse events and deviations are reported to the IRB per current guidelines and stored appropriately
- All versions of the IRB protocols and informed consent forms are on file

INFORMED CONSENT.

- Ensure that participant identification is not recorded on the ICF (i.e., no participant ID)
- There is documentation that the participant is given a copy of the consent form
- The participant and study representative signed and dated the consent form for him/herself
- The participant initialed and dated all appropriate pages on the informed consent form
- Note to file (Appendix F) made for any informed consent deviations
- Ensure a valid (current version date) copy of the consent form was used

PROTOCOL DEVIATIONS.

- Any and all protocol deviations (exceptions and violations) are documented in the participant folder and reported to the IRB as required

OTHER SOURCE DOCUMENTS.

- Each participant folder will contain a checklist to ensure that all source documents are administered and collected properly. The checklist will be dated by the researcher for each time an assessment is administered
- Review participant folders to ensure the accuracy, completeness, and legibility of the data.
- Any correction made to the source documents is dated, initialed, and explained. The original entry should not be obscured.
- The protocol-specific source documents are on file.
- Source documents are completed in ink.
- Note to files (Appendix F) are made for missing or incomplete data and to explain any discrepancies or additional comments.

DNA.

- Participant names will not be on any of the samples collected. DNA is sequenced to check for one nucleotide. When testing is performed, only de-identified information is shared with an outside party. This information will not be shared with anyone outside of the study personnel, including the participant.

